6.6.1. Corneal Supportive Care Guidelines for Belantamab Mafodotin

Changes in visual acuity, which commonly manifests as changes in corneal epithelium observed on ocular examination, have been observed with antibody drug conjugates, including those conjugated to MMAF [Eaton, 2015].

Sites are required to establish a close collaboration with an ophthalmologist (or optometrist, if an ophthalmologist is not available) who will be responsible for assessing participants and managing those who develop corneal epithelium on ocular examination in close communication with GSK Medical Monitor.

Participants will be assessed by an ophthalmologist (or an optometrist if an ophthalmologist is not available) baseline and every three weeks. If there are no corneal examination findings (Grade 2 or above) at time of the Cycle 6 exam, participants may

have their ophthalmologic exams decreased to once every 3 months. In case of persistent ocular exam findings, newly developed ocular symptoms or vision changes, further ocular exams should be performed at least every cycle until resolution (to Grade 1 or baseline) or more frequently as clinically indicated by the qualified eye care specialist (Appendix 9). See Section 8.3.9 for the list of ophthalmic exam procedures.

Participants who have ocular symptoms at end of study treatment will continue to be followed as indicated in the SoA (Section 1.3) for up to 12 months, or until full resolution of findings: defined as a return to participant's baseline, or until deemed clinically stable by an ophthalmologist (or an optometrist if an ophthalmologist is not available), whichever comes first. Clinically stable is defined as changes less than or equal to Grade 1 as per Table 7.

Prophylactic preservative-free artificial tears should be administered in each eye at least 4 to 8 times daily, beginning on Cycle 1 Day 1 until EOT. Allow at least 5-10 minutes between administration of artificial tears and steroid eye drops (if administered). In the event of ocular symptoms (e.g., dry eyes), the use of artificial tears may be increased up to every 2 hours as needed.

While not yet clinically demonstrated, it is possible that the application of a cooling eye mask during belantamab mafodotin administration, and in the first few hours after infusion may subsequently decrease ocular side effects. On the day of infusion, at the discretion of the participant and the investigator, the following may be considered:

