8.3.3. Follow-up of AEs and SAEs

After the initial AE/SAE report, the investigator is required to proactively follow each participant at subsequent visits/contacts. All SAEs, non-serious AEs of special interest, will be followed until the event is resolved, stabilised, otherwise explained, or the participant is lost to follow-up (as defined in Section 7.3). Further information on follow-up procedures is given in Appendix 3.

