3.2. Final Analyses

The final planned primary analyses will be performed after the completion of the following sequential steps:

1. All participants have completed the study as defined in the protocol, i.e., when all participants have progressed, died, withdrawn consent, discontinued treatment due to other reasons, or have been lost to follow-up.
2. All required database cleaning activities have been completed and final database release (DBR) and database freeze (DBF) has been declared by Data Management.

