8.3. Adverse Events of Special Interest Analyses

Adverse events of special interest (AESI) for belantamab mafodotin are corneal events, thrombocytopenia and infusion related reactions.

Summaries of the number and percentage of participants with these events will be provided for each type of events separately by preferred term and maximum grade. The time of onset and duration of first occurrence of corneal events will be summarized using summary statistics mean, standard deviation, median, minimum value, and maximum. The number and percentage of participants who have time of onset of first occurrence (1-21, 22-42, 43-63, >63 days) will be reported. The number and percentage of participants who have duration of first occurrence (1-21, 22-42, >42 days) will be reported.

The summary of event characteristics of corneal events and thrombocytopenia will also be provided, including number of participants with any event, number of events, number of participants with any event that is serious, number of participants with any event that is related to study treatment, number of occurrences (One, Two, Three or more), maximum grade and the action taken for the event. The percentage will be calculated in two ways, one with number of participants with event as the denominator and the other with total number of participants as the denominator. The worst-case approach will be applied at participant level for the maximum grade, i.e. a participant will only be counted once as the worst case from all the events experienced by the participant. For action taken to an event, participant will be counted once under each action, e.g. if a participant has an event leading to both study treatment discontinuation and dose reduction, the participant will be counted once under both actions.

A comprehensive list of MedDRA terms based on clinical review will be used to identify each type of event. The details of the planned displays are provided in [Appendix 12: List of Data Displays](#).

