14.7.2.1. Handling of Missing and Partial Dates

Element	Reporting Detail
General	
 Partial dates will be displayed as captured in participant listing displays. Imputed partial dates will not be used to derive study day, duration (e.g. duration of adverse events), or elapsed time variables. In addition, imputed dates are not used for deriving the last contact date in the overall survival analysis dataset. Imputed dates will not be displayed in listings. However, where necessary, display macros may impute dates as temporary variables for the purpose of sorting data in listings only. In addition, partial dates may be imputed for 'slotting' data to study time periods or for specific analysis purposes as outlined below.
Adverse Events	
 The eCRF allows for the possibility of partial dates (i.e., only month and year) to be recorded for AE start and end dates; that is, the day of the month may be missing. 
 Missing Start Day: First of the month will be used unless this is before the start date of study treatment; in this case the study treatment start date will be used and hence the event is considered On-treatment as per Appendix 4: Study Phases and Treatment Emergent Adverse Events. Missing Stop Day: Last day of the month will be used. Completely missing start dates will remain missing, with no imputation applied. Consequently, time to onset and duration of such events will be missing. Completely missing end dates will remain missing, with no imputation applied. Consequently, duration of such events will be missing.
Concomitant Medications/Medical History	
 Partial dates for any concomitant medications recorded in the CRF will be imputed using the following convention: 
 If the partial date is a start date, a '01' will be used for the day and 'Jan' will be used for the month If the partial date is a stop date, a '28/29/30/31' will be used for the day (dependent on the month and year) and 'Dec' will be used for the month. The recorded partial date will be displayed in listings.
Covariates for efficacy analysis (Date of initial diagnosis/ Last recurrence/ Last progression)	
 If both month and day are missing, first of January will be used If only day is missing, first of the month will be used

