14.12.10. Safety Tables

Safety: Tables					
No.	Population	GSK Standard/ Example Shell	Title	Programming Notes	Deliverable [Priority]
Adverse Events (AEs)					
4.010	All Treated	AE13	Adverse Event Overview		SAC [1]
4.020	All Treated	AE3	Summary of All Adverse Events by Preferred Term		SAC [1]
4.030	All Treated	OAE07	Summary of All Adverse Events by Preferred Term and Maximum Grade		SAC [1]
4.040	All Treated	OAE07	Summary of All Treatment-Related Adverse Events by Preferred Term and Maximum Grade		SAC [1]
4.050	All Treated	OAE07	Summary of Non-Serious Adverse Events by Preferred Term and Maximum Grade		SAC [1]
4.060	All Treated	AE3	Summary of Adverse Events of Maximum Grade 3 or Higher by Preferred Term		SAC [1]
Adverse Events of Special Interest					
4.070	All Treated	OAE07	Summary of Corneal Events by Preferred Term and Maximum Grade		SAC [1]
4.080	All Treated	OAE07	Summary of Thrombocytopenia by Preferred Term and Maximum Grade		SAC [1]
4.090	All Treated	OAE07	Summary of Infusion Related Reactions by Preferred Term and Maximum Grade		SAC [1]
4.100	All Treated	ESI2b	Summary of Onset and Duration of the First Occurrence of Corneal Events		SAC [1]
4.110	All Treated	ESI1	Summary of Characteristics of Corneal Events		SAC [1]
4.120	All Treated	ESI1	Summary of Characteristics of Thrombocytopenia		SAC [1]
4.130	All Treated	AE3	Summary of Corneal Events Leading to Dose Modification by Preferred Term		SAC [1]
Serious and Other Significant Adverse Events					
4.140	All Treated	AE3	Summary of Serious Adverse Events by Preferred Term		SAC [1]
4.150	All Treated	AE3	Summary of All Treatment-Related Serious Adverse Events by Preferred Term		SAC [1]

CONFIDENTIAL

208465

Safety: Tables					
No.	Population	GSK Standard/ Example Shell	Title	Programming Notes	Deliverable [Priority]
4.160	All Treated	AE1	Summary of Adverse Events Leading to Dose Modification by System Organ Class and Preferred Term		SAC [1]
Laboratory: Chemistry					
4.170	All Treated	OLB9B	Summary of Chemistry Worst Grade Changes from Baseline Grade		SAC [1]
Laboratory: Hematology					
4.180	All Treated	OLB9B	Summary of Hematology Worst Grade Changes from Baseline Grade		SAC [1]
Laboratory: Hepatobiliary (Liver)					
4.190	All Treated	LIVER10	Summary of Hepatobiliary Laboratory Abnormalities		SAC [1]
ECG					
4.200	All Treated	EG1	Summary of ECG Findings		SAC [1]
4.210	All Treated	OECG1B	Summary of Worst-case Increases in Fridericia's QTc		SAC [1]

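### A first corneal event still ongoing at last assessment gets no duration, so Table 4.100 omits it from the duration statistics and from the >42 days row even when it has already been observed for longer than 42 days

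*SAP*

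**What the plan says.** SAP 8.3 covers the adverse events of special interest, of which corneal events are one. The "duration of first occurrence of corneal events will be summarized using summary statistics mean, standard deviation, median, minimum value, and maximum". The same paragraph continues: "The number and percentage of participants who have duration of first occurrence (1-21, 22-42, >42 days) will be reported". The display is Table 4.100 in SAP 14.12.10, "Summary of Onset and Duration of the First Occurrence of Corneal Events", on the All Treated population, with no programming note.

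The rule for events without an end date is in the Adverse Events row of SAP 14.7.2.1: "Completely missing end dates will remain missing, with no imputation applied. Consequently, duration of such events will be missing".

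On follow-up, Protocol 6.6.1 keeps participants who have ocular symptoms at the end of treatment under observation "for up to 12 months, or until full resolution of findings", or until clinically stable, whichever is first. It defines clinically stable as changes of Grade 1 or less. Protocol 8.3.3 says that events of special interest "will be followed until the event is resolved, stabilised, otherwise explained, or the participant is lost to follow-up".

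**The concern.** An ongoing event has a start date and a last assessment but no end date. Under the SAP rule its duration is missing, so it contributes to nothing in the duration part of Table 4.100. For the mean and median this amounts to analysing resolved events only. For the >42 days row it discards a known fact: an event seen on day 100 and not yet resolved has certainly lasted more than 42 days.

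Table 4.100 is the only planned summary table of how long first corneal events last. Protocol 2.3.2 names corneal events as the most frequently reported adverse events with this drug. It gives a median time to resolution of 91 days for Grade 2 or above findings, so the >42 days row is where much of the information would be expected to fall.

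**Working it through.** **Step 1. Does any other rule cover an ongoing event?** The places where the SAP deals with open-ended records are these:
- SAP 7.2 plans Kaplan-Meier, but for duration of response only.
- SAP 14.4.1 has conventions for ongoing subjects, but they assign concomitant medications to study periods.
- SAP 14.7.2.1 imputes a missing treatment end date for participants still on treatment, but only at an interim analysis and only for exposure.
- Table 4.100 has no programming note. Its shell is in a separate document (SAP 14.13) and cannot be seen.

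None of these gives an ongoing adverse event a duration. A line in the shell for n or for missing values would show that events are absent. It would not move them into the >42 days row.

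**Step 2. Direction.** An omitted event observed for more than 42 days lowers the count by one. An omitted event observed for 42 days or less does not make the count wrong, because its final category is unknown. The error in the count is therefore zero or negative, whatever the duration distribution.

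**Step 3. Size of one miscounted event.** The plan states no figure to reproduce. Inputs:
- one cohort of up to six (Protocol 4.1), because the 3.4 mg/kg cohort is optional (Protocol 2.4.2);
- keratopathy in 71% at 2.5 mg/kg in the earlier phase II study (Protocol 2.3.2).

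Expected first events: 0.71 × 6 = 4.26, taken as 4.

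SAP 8.3 states no denominator for the duration rows. For the event-characteristics summary in the same section it gives two: "one with number of participants with event as the denominator and the other with total number of participants as the denominator". Three possibilities are therefore shown:
- participants with an event: 1/4 = 25.0 points;
- all treated: 1/6 = 16.7 points;
- events with a known duration, where k of the 4 truly exceed 42 days including the ongoing one: k/4 − (k−1)/3 = 25.0, 16.7, 8.3 and 0 points for k = 1, 2, 3, 4.

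**Step 4. How likely, and how short is the median?** The documents do not give the unresolved share u, so it is assumed. The underlying median is assumed to be 91 days. That figure is for Grade 2 or above findings in another study, and Protocol 2.3.2 does not say how unresolved findings were treated in it. Two mechanisms bracket the result.

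*A: the longest events are the unresolved ones, all past day 42.*
- P(at least one of 4) = 1 − (1−u)^4.
- Resolved-only median, exponential: 91 × ln[1/(1 − 0.5(1−u))]/ln 2.
- Resolved-only median, log-normal: 91 × exp[s·Φ⁻¹(0.5(1−u))], with s = 0.8 or 0.5.

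*B: follow-up ends independently of the event (exponential event and censoring times).*
- Resolved-only median = 91(1−u).
- Share of ongoing events already past day 42: q = 0.5^(42/[91(1−u)]).
- P(at least one of 4) = 1 − (1 − uq)^4.

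| u (assumed) | P(≥1 miscounted), A | q | P(≥1 miscounted), B | Median shortening, A (exponential / s=0.8 / s=0.5) | Median shortening, B |
|---|---|---|---|---|---|
| 5% | 18.5% | 0.714 | 13.5% | 6.4 / 4.5 / 2.8 d | 4.6 d |
| 10% | 34.4% | 0.701 | 25.2% | 12.5 / 8.7 / 5.5 d | 9.1 d |
| 25% | 68.4% | 0.653 | 51.0% | 29.3 / 20.5 / 13.4 d | 22.8 d |

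Check at u = 10%. Mechanism A: 1 − 0.9^4 = 0.344. Mechanism B: 91 × 0.9 = 81.9 days; q = 0.5^(42/81.9) = 0.701; 1 − (1 − 0.0701)^4 = 0.252.

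These are large-sample medians. With about 4 events the sample median varies widely in any case.

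**The case against.** **The missing-date rule may not be meant for ongoing events.** SAP 14.7.2 describes missing data as requested data that were not provided, and the documents do not show whether the case report form requests an end date for an ongoing event. That is fair. But a duration cannot be computed without an end date, and no other rule supplies one. On this reading the SAP is silent instead of explicit, and the events are still left out.

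**The shell may already label the statistics.** This stands. One might infer that the table presents resolved-only figures without saying so. The shell is not available, so that cannot be asserted.

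**Unresolved events may be rare.** This largely stands. Three stronger readings are tempting, and the documents do not support them:
- *Follow-up that stops at stabilised leaves many events open.* Protocol 6.6.1 defines clinically stable as Grade 1 or less. Footnote 7 of the Schedule of Activities describes resolution as a return to Grade 1 or baseline. Some such events may be closed with an end date, although the documents do not say so.
- *The final analysis may fall as soon as the last participant stops treatment.* SAP 3.2 allows it "when all participants have progressed, died, withdrawn consent, discontinued treatment due to other reasons, or have been lost to follow-up". It also requires that participants have completed the study, and SAP 14.7.1 describes completion as all scheduled visits plus the exit visit. The two participants still on treatment at Amendment 3 say nothing about whether a first event is open. Longer treatment also lengthens the observation of a first event.
- *Half of the events could be unresolved.* Nothing in the documents supports a share of that size, so it is not used.

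The remaining routes are the 12-month cap on post-treatment ocular follow-up, death, withdrawal and loss to follow-up. The cap runs from the end of treatment, so full follow-up of an on-treatment event lasts at least 12 months from onset.

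**The model is rough.** An exponential with a 91-day median puts 0.5^(201/91) = 22% of events beyond 201 days, the longest time reported in Protocol 2.3.2. This is why the log-normal versions are shown. The direction of the count error needs no model.

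**Little depends on this table.** Duration is not a listed endpoint, and the analysis is descriptive. Tables 4.070 and 4.110 still count ongoing events, and Listings 1.130 and 1.200 show each one. This settles the severity.

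**Conclusion.** The concern holds as a minor one. Under SAP 14.7.2.1 read with SAP 8.3, a first corneal event ongoing at last assessment is left out of the duration statistics and of every duration row, including >42 days when it has already passed that point. The count can only be too low, and the resolved-only mean and median will tend to be short.

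One miscounted event among about 4 costs 25, 17 or 0 to 25 points, depending on the denominator. At an assumed 10% unresolved, the chance of at least one is about 25-34% and the median is about 5 to 13 days short. These sizes rest on the assumed share, on the 91-day median taken from another study, on the assumed distributions, and on a single cohort of six.

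A reader might infer that ongoing corneal events are certain, or that they disappear from the report. Neither follows: the protocol makes them possible only, and the incidence tables and listings retain them.

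**What to change.** In SAP 8.3 and in a programming note to Table 4.100:
1. Count an ongoing first corneal event already observed beyond 42 days in the >42 days row, taking the time to last assessment as its minimum duration.
2. Show the number of first events ongoing at last assessment, with their observed time.
3. Label the mean, SD, median, minimum and maximum as resolved events only, unless the shell already does so.

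Naming the denominator of the duration rows in the same place, if the shell does not, would remove the ambiguity in the percentages.

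The cost is one changed table and two or three SAP sentences. No new data are needed, and no other planned summary is affected.

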8.6. Pregnancies

While pregnancy itself is not considered to be an AE or SAE, any pregnancy complication or elective termination of a pregnancy for medical reasons will be recorded as an AE or SAE as described in the protocol. If participants and participants’ partner become pregnant while on the study, the information will be included in the narratives and no separate table or listing will be produced.

8.7. Clinical Laboratory Analyses

Only local laboratory evaluations including the analyses of Chemistry laboratory tests, Haematology laboratory tests, Urinalysis, and liver function tests will be based on GSK Core Data Standards. The details of the planned displays are in [Appendix 12: List of Data Displays](#).

Summaries of worst case grade increase from baseline grade will be provided for all the lab tests that are gradable by CTCAE v5.0. These summaries will display the number and percentage of participants with a maximum post-baseline grade increasing from their baseline grade. Any increase in grade from baseline will be summarized along with any increase to a maximum grade of 3 and any increase to a maximum grade of 4. Missing baseline grade will be assumed as grade 0. For laboratory tests that are graded for both low and high values, summaries will be done separately and labelled by direction, e.g., sodium will be summarized as hyponatremia and hypernatremia.

Separate summary tables for haematology, and chemistry laboratory tests will be produced. Liver function laboratory tests will be included with chemical chemistry.

A supporting listing of laboratory data for subjects with abnormalities of potential clinical concern will be provided. A separate listing of laboratory data with character values will also be provided. For lab test values that can be graded, values of grade 1 or above are defined as values of potential clinical concern. For lab test values that cannot be graded, values out of the normal range are defined as values of potential clinical concern.

Detailed derivation of baseline assessment is specified in Section 5.2.

Unless otherwise specified, the denominator in percentage calculation at each scheduled visit will be based on the number of participants with non-missing value at each particular visit.

8.7.1. Analyses of Liver Function Tests

Summaries of hepatobiliary laboratory events including possible Hy's law cases will be provided in addition to what has been described above.

8.8. Other Safety Analyses

The analyses of non-laboratory safety test results including ECGs, ECHOs, Ocular findings and vital signs will be based on GSK Core Data Standards, unless otherwise specified. The details of the planned displays are presented in [Appendix 12: List of Data Displays](#).

Unless otherwise specified, the denominator in percentage calculation at each scheduled visit will be based on the number of participants with non-missing value at each particular visit.

8.8.1. Performance Status

A ECOG performance status listing will also be provided.

8.8.2. ECG

A summary of the number and percentage of participants who had normal and abnormal (clinically significant and not clinically significant) ECG findings will be displayed by scheduled visits as well as for the worst case post-baseline.

The QTc values based on Fridericia formula will be rounded to the integer and the values will be categorized into the following CTCAE grade and ranges: Grade 0 [REDACTED] Grade 1 [REDACTED] Grade 2 [REDACTED] and Grade 3 [REDACTED] Summaries of grade increase will be provided. These summaries will display the number and percentage of participants with any grade increase, increase to grade 2 and increase to grade 3 in the worst case post-baseline only.

A listing of QTc values of potential clinical importance will be provided.

The summaries and listing of QTc will use the collected values based on Fridericia formula.

9. IMMUNOGENICITY / BIOMARKER ANALYSES

For each participant, the anti-belantamab mafodotin (drug) antibody results, titers, and also ADC and total antibody concentration will be listed for each assessment time point. The frequency and percentage of participants with positive and negative anti-drug antibody will be summarized for each assessment time and overall for each participant. The conclusive results will be based on the total antibody concentration. The details of the planned displays are presented in [Appendix 12: List of Data Displays](#).

Summary of biomarker change from baseline by scheduled visits using mean, median, standard deviation, minimum and maximum will be provided. A listing of biomarker will be provided. The details of the planned displays are presented in [Appendix 12: List of Data Displays](#).

